9.2 DISCUSSION OF STUDY DESIGN, INCLUDING THE CHOICE OF CONTROL GROUPS

The double-blind design was adopted to minimize systematic bias resulting from the Investigator or the patient knowing the treatment being administered. Randomization is expected to minimize patient selection bias and increase baseline comparability among the treatment groups. The doses of cariprazine under study were chosen on the basis of experience from the RGH-MD-52 and RGH-MD-56 studies (see Section 7.0), as well as experience in the cariprazine development program in healthy volunteers and patients with other indications and other atypical antipsychotics for the treatment of bipolar depression. The use of a placebo control is critical to the study to allow discrimination of patient outcomes caused by the individual dose levels of cariprazine from outcomes caused by other factors (e.g., the observer or patient expectations, the natural progression of the disease, the conditions of being in a study).

No double-blind down-taper has been included as cessation of cariprazine at doses comparable to those under study has not given rise to appreciable discontinuation symptoms.

9.3 SELECTION OF STUDY POPULATION

9.3.1 Inclusion Criteria

To be eligible to participate in the study, patients must meet the following criteria:

Inclusion criteria to be assessed at Visit 1 (Screening)

- 1. Written informed consent, signed, obtained from the patient before the initiation of any study-specific procedures
- 2. Male or female patients 18 to 65 years of age, inclusive
- 3. Currently meet the DSM-5 criteria for bipolar I disorder without psychotic features confirmed by the administration of the Mini International Neuropsychiatric Interview (MINI), with a current major depressive episode of at least 4 weeks and not exceeding 12 months in duration
- 4. Currently treated as an outpatient at the time of enrollment
- 5. A verified previous manic or mixed episode. Verification must include one of the following sources:
 - a. Treatment of mania with an anti-manic agent (eg, lithium or divalproate) or antipsychotic medication with an approved indication for mania
 - b. Hospital records/Medical records
 - c. Patient report corroborated by caretaker or previous or current treating clinician
- 6. 17-item Hamilton Depression Rating Scale (HAMD-17) total score ≥ 20
- 7. HAMD-17 item 1 score ≥ 2
- 8. CGI-S score ≥ 4
- 9. Negative serum β-human chorionic gonadotropin (β-hCG) pregnancy test (women of childbearing potential only)
- 10. Normal physical examination, clinical laboratory test results, and electrocardiogram (ECG) results or abnormal findings that are judged not clinically significant by the PI

Inclusion criteria to be assessed at Visit 2 (Baseline)

11. Continue to meet Visit 1 inclusion criteria

9.3.2 Exclusion Criteria

Patients who meet any of the following criteria will not be eligible to participate in the study:

Exclusion criteria to be assessed at Visit 1 (Screening)

Psychiatric Criteria

- 1. Young Mania Rating Scale (YMRS) total score > 12
- 2. Four or more episodes of a mood disturbance (depression, mania, hypomania, or mixed state) within the 12 months before Visit 1
- 3. Any current axis 1 psychiatric diagnosis other than bipolar disorder with the exception of specific phobias
- 4. History of meeting DSM-5 criteria for:
 - o Dementia, amnesic, or other cognitive disorder
 - Schizophrenia, schizoaffective, or other psychotic disorder
 - Mental retardation
- 5. DSM-5—based diagnosis of borderline or antisocial personality disorder or other axis II disorder of sufficient severity to interfere with participation in this study
- 6. History of meeting DSM-5 criteria for substance-related disorders (excluding caffeine-related and tobacco-related disorders) within the 6 months before Visit 1
- 7. Positive result on blood alcohol test or urine drug screen for any prohibited medication. Exception:
 - o patients with a positive cannabinoid on entry may be retested before randomization. If the patient remains positive, the patient is no longer eligible
 - o patients positive for opiates on entry, discussion with Study Physician is required.

Treatment-Related Criteria:

- 14. Electroconvulsive therapy in the 3 months before Visit 1
- 15. Previous lack of response to electroconvulsive therapy
- 16. Treatment with a depot antipsychotic drug within 6 months prior to Visit 1
- 17. Treatment with clozapine in a dose of > 50 mg/day in the past 2 years

19. Previous treatment with vagus nerve stimulation or transcranial magnetic stimulation within 6 months before Visit 1

[figure not shown]
- 20. Prior participation with any clinical trials, involving experimental or investigational drugs, within 6 months before Visit 1 or during the study
- 21. Initiation or termination of psychotherapy for depression within the 3 months preceding Visit 1, or plans to initiate, terminate, or change such therapy during the course of the study.
- 22. Initiation or termination of phototherapy within the 2 weeks before screening, or plans to initiate same during the course of the study

Other Medical Criteria:

- 24. Female patients who meet the following criteria:
 - Pregnant, breastfeeding, or planning to become pregnant or breastfeed during the study

- 32. Known history of cataracts or retinal detachment
- 33. Known human immunodeficiency virus infection

Other Criteria:

38. Employee, or immediate relative of an employee, of the Sponsor, any of its affiliates or partners, or the study center

9.3.3 Removal of Patients from Therapy or Assessment

A premature discontinuation will occur when a patient who signed the ICF ceases participation in the study, regardless of circumstances, before the completion of the protocol. Patients can be prematurely discontinued from the study for one of the following reasons:

- Screen Failure (Failure to meet inclusion/exclusion criteria)
- Withdrawal of consent.
- Adverse event
- Lack of Efficacy
- Protocol violation
- Non-compliance with Study Drug
- Lost to follow-up
- Study terminated by Sponsor
- Site terminated by Sponsor
- Other

A patient completing Visits 1 through 6 will be considered a completer. All randomized patients who prematurely discontinue from the study, regardless of the cause, should be seen for a final assessment at an early termination (ET) visit. A final assessment will be defined as completion of the evaluations scheduled for Visit 6/ET). All investigational products dispensed at earlier visits that had not been previously collected should be collected at the final visit. Patients refusing to come in for a final visit must be requested in writing, with a registered letter, to come in for an ET visit and to return any unused investigational product. A copy of the letter, together with the source documentation, will be kept by the Investigator. The reasons for premature discontinuation from the study will be reflected on the study termination record of the eCRF.

Patients with Visit 6/ET more than 4 days after the last dose of double-blind investigational product will be administered safety assessments only.

9.3.4 Patient Replacement Procedures

Patients in this study who prematurely discontinue treatment will not be replaced.

[figure not shown]
9.4 TREATMENTS

9.4.1 Treatments Administered

Investigational product in the form of capsules packaged in blister packs will be provided by the Sponsor. No investigational product will be administered during the screening period or the safety follow-up period. For the 6-week double-blind treatment period, patients will be supplied with identically appearing capsules of either cariprazine or placebo.

9.4.2 Identity of Investigational Product(s)

Investigational product will be supplied in blister packs containing 10 capsules and will be labeled with the protocol number, the visit number/space to write visit number, storage information, warning language (viz, "Caution: New Drug—Limited by Federal Law to Investigational Use"), and instructions to take the capsules once daily as directed, and the medication identification number. Investigational product labels will be country specific. Immediately before dispensing the investigational product, the Investigator will write the patient's initials, site number, and date on the label.

The Investigator is responsible for recording the receipt and use of all investigational products supplied and for ensuring the supervision of the storage and allocation of these supplies. All unused investigational products must be returned; and, whenever investigational products are returned, unit counts must be performed. All investigational products must be accounted for. At the end of the study, or upon drug expiration, any unused investigational product must be returned to the Sponsor or Sponsor's designee.

9.4.3 Method of Assigning Patients to Treatment Groups

Each study center will be provided with investigational products. An interactive voice/interactive Web response system (IxRS) will be used during the study to monitor enrollment and medication allocation. If the patient meets the randomization criteria, the study center will contact the IxRS at end of Visit 2 to randomize the patient. IxRS will randomize the patient to the appropriate treatment arm (placebo, cariprazine 1.5 mg/day, or cariprazine 3.0 mg/day) and determine the investigational product number to be assigned to the patient based on the randomization.

9.4.4 Selection of Dosages in the Study

The doses of cariprazine selected for this study were based on the results from 2 completed studies in patients with bipolar depression (RGH-MD-52 and RGH-MD-56), as well as experience in the cariprazine development program in healthy volunteers and patients with other indications and other atypical antipsychotics for the treatment of bipolar depression. Study RGH-MD-52 indicated numerically better results for the high-dose cariprazine group (1.5-3.0 mg/day) relative to placebo up to end of Week 6. In the cariprazine low-dose group (0.25-0.75 mg/day), better efficacy was observed following a dose increase, and tolerability was not compromised. Thus, cariprazine 0.75, 1.5, and 3.0 mg/day were selected for further evaluation in Study RGH-MD-56.

In Study RGH-MD-56, for both the primary and secondary efficacy parameters, change from baseline in MADRS total score and CGI-S score at Week 6, statistically significant improvement was demonstrated for the cariprazine 1.5 mg dose relative to placebo. Nominally significant improvement was shown for cariprazine 3 mg, which did not remain statistically significant after adjusting for multiplicity. No statistically significant treatment effect was shown for the 0.75 mg dose at Week 6. A post-hoc analysis of patients who completed the full 8 weeks of treatment (completer population) in Study RGH-MD-56 demonstrated similar reductions from baseline relative to placebo in MADRS total score for the cariprazine 1.5 and 3 mg/day groups at Week 6 and Week 8.

The primary efficacy results and the post-hoc completers analysis in Study RGH-MD-56 led to the selection of the cariprazine 1.5 and 3 mg/day doses for further evaluation in this study. A dose higher than 3 mg/day was not chosen because of concerns related to the potential for higher extrapyramidal symptom rates with increasing cariprazine dose.

A fixed-dose regimen allows for unambiguous evaluation of safety and efficacy of individual doses

9.4.5 Selection and Timing of Dose for Each Patient

All investigational products will be dispensed in blister packs. Each blister pack will contain 10 capsules arranged in 10 columns and 1 row, adequate for the 7 days of the week plus 3 extra days. The configuration of the blister packs is provided in Table 9.4.5–1.

At Visit 2, patients who continue to meet all eligibility criteria will be assigned a randomization number and dispensed a corresponding blister pack of double-blind investigational product for the first week of double-blind treatment. Patients will be instructed to take 1 capsule daily, in order from left to right of the blister pack, beginning on the evening of Visit 2 or the morning after Visit 2

At Visit 3 (end of week 1 of double-blind treatment) patients will be dispensed 1 blister pack. At Visits 4 and 5 (end of week 2 and end of week 4 of double-blind treatment), patients will be dispensed 2 blister packs.

All patients randomized to cariprazine dose groups will receive cariprazine 1.5 mg/day for 2 weeks, from Day 1 through Day 14. For patients randomized to the cariprazine 3.0 mg/day group, the dose will be increased to 3.0 mg/day on Day 15.

Drug holidays (up to a maximum of 3 consecutive days) are allowed if there are tolerability problems at the discretion of the Investigator. Patients unable to tolerate the fixed dose of the investigational product or patients off drug for 4 or more consecutive days will be prematurely discontinued from the study.

All investigational products will be taken orally as a single daily dose at approximately the same time of day (morning or evening). The dosing time can be switched if there are tolerability problems. Any switch must allow at least 24 hours between 2 consecutive doses and must be documented in the eCRF.

At each visit, patients will be instructed to return all unused investigational product.

	Visit 2 Days 1-7 + 3 extra days	Visit 3 Days 8-14 + 3 extra days	Visit 4 Days 15-28 + 6 extra days	Visit 5 Days 29-42 + 6 extra days
Treatment group: placebo				
Row 1	0 mg	0 mg	0 mg	0 mg
Treatment group: cariprazine 1.5 mg/day				
Row 1	1.5 mg	1.5 mg	1.5 mg	1.5 mg
Treatment group: cariprazine 3.0 mg/day				
Row 1	1.5 mg	1.5 mg	3.0 mg	3.0 mg

Table 9.4.5–1. Blister Card Configuration and Dosing Regimen

Note: At Visit 2 and Visit 3 patients will be dispensed 1 blister pack. At Visit 4 and Visit 5, patients will be dispensed 2 blister packs. Each blister pack will contain 10 capsules, adequate for 7 days plus 3 extra days.

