9.4.9 Monitoring Treatment Compliance

Investigational product compliance will be monitored by counting the number of capsules dispensed and the number returned by the patient. Before new investigational product is dispensed at any visit, every effort will be made to collect all unused investigational product. If a patient demonstrates poor compliance at any time during the study (< 80% or > 120% measured by pill counts), then they should be discontinued from the study.

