9.7.4.2 Measurement of Treatment Compliance

Dosing compliance for a specified period is defined as the total number of capsules actually taken by a patient during that period divided by the number of capsules that were expected to be taken during the same period multiplied by 100. The total number of capsules actually taken during a specific period is calculated as the number of days in that period multiplied by the number of capsules taken each day during that period. The number of capsules expected to be taken for a specific treatment period will be calculated by multiplying the number of days in that period by the number of capsules to be taken per day. Descriptive statistics for investigational product compliance will be presented by treatment group for each period between 2 consecutive visits, as well as for the whole double-blind treatment period of the study for the Safety Population.

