5.1.1.4.1 Study Treatment Exposure and Compliance

Study treatment exposure and compliance will be summarized by treatment group for the Safety Population as follows:

Table 5-15 Study Treatment Summaries

Parameter	Description	Timing	Methodology
Study treatment exposure (days)	Treatment end date - treatment start date + 1	Treatment Period	Continuous descriptives
Patient-years of study treatment exposure (years)	Sum over participants of study treatment exposure	Treatment Period	—

Parameter	Description	Timing	Methodology
Study treatment compliance (%)	
Summary by visit interval and overall
 $100 \times \frac{\text{Number of capsules actually taken}}{\text{Number of capsules expected to be taken}}$ 
 The total number of capsules actually taken during a specific period is calculated as the sum of the number of capsules taken during that interval. The number of capsules expected to be taken for a specific interval will be calculated by multiplying the number of days in that period by the number of capsules to be taken per day. 	
Week 0 (Baseline)-Week 1 visit (not inclusive), Week 1 visit-Week 2 visit (not inclusive), Week 2 visit-Week 4 visit (not inclusive), Week 4 visit-Week 6 visit (not inclusive), and Overall Treatment Period
	Continuous descriptives

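### Protocol 9.4.5 permits 3-day drug holidays, but one completed by Day 14 falls below the 80% pill count at which 9.4.9 says a patient should be discontinued

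*Protocol*

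**What the plan says.** Protocol 9.4.5 sets a holiday rule and a limit on it. The permission reads "Drug holidays (up to a maximum of 3 consecutive days) are allowed if there are tolerability problems at the discretion of the Investigator". The limit is that "patients off drug for 4 or more consecutive days will be prematurely discontinued from the study".

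Protocol 9.4.9 sets a separate rule based on capsule counts: "If a patient demonstrates poor compliance at any time during the study (< 80% or > 120% measured by pill counts", and for such a patient the text continues "then they should be discontinued from the study". Neither section refers to the other.

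A count should exist at every visit. Section 9.4.5 says "At each visit, patients will be instructed to return all unused investigational product", and section 9.4.2 adds that "whenever investigational products are returned, unit counts must be performed".

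Compliance formulas appear only for descriptive summaries. Protocol 9.7.4.2 reports compliance "for each period between 2 consecutive visits, as well as for the whole double-blind treatment period of the study". SAP 5.1.1.4.1 obtains the expected number of capsules by "multiplying the number of days in that period by the number of capsules to be taken per day", and the protocol uses the same denominator. Neither formula subtracts holiday days.

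**The concern.** The two sections can give opposite answers for the same patient. A patient who pauses for 3 days for tolerability, with the Investigator's agreement, stays in the study under 9.4.5. If the pill count then reads below 80%, 9.4.9 taken literally says the patient should leave. Because 9.4.9 gives no counting period and no exemption, each site has to choose a reading.

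The stake is follow-up to the primary time point. A patient discontinued at Visit 3 or 4 has an early termination visit (Protocol 9.3.3) and one further week of safety follow-up (Protocol 9.1). The visible text provides for no Week 6 MADRS in that patient. Earlier scores still enter the primary model, which uses all observed postbaseline values without imputation (Protocol 9.7.5.1). Holidays are granted for tolerability problems, so the patients exposed to the conflict are those the holiday rule is meant to keep on study.

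**Working it through.** The documents give no compliance percentage for a holiday, so there is no figure of the plan's to reproduce.

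**Inputs.** One capsule a day, and intervals of Days 1-7, 8-14, 15-28 and 29-42, closed by Visits 3, 4, 5 and 6 (Protocol 9.4.5 and Table 9.4.5-1). The holiday is 3 consecutive days (9.4.5) and the limit is 80% (9.4.9). A 3-day holiday can start on any of Days 1 to 40, giving 40 start days.

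**Formulas.**
- Per interval of length L: (L − days off in the interval) / L.
- Cumulative at visit day D: (D − days off up to D) / D, for D = 7, 14, 28, 42.
- Whole period: (42 − 3) / 42 = 92.9%.

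A holiday lying wholly inside one interval breaches when (L − 3)/L < 0.80, that is, when L < 15. All four nominal intervals are shorter than 15 days.

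**Results.** Lowest value for each start day:

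| Start day | Per interval | Cumulative |
|---|---|---|
| 1-5 | 4/7 = 57.1% (Visit 3) | 4/7 = 57.1% (Visit 3) |
| 6 | 5/7 = 71.4% (Visit 3) | 5/7 = 71.4% (Visit 3) |
| 7 | 5/7 = 71.4% (Visit 4) | 11/14 = 78.6% (Visit 4) |
| 8-12 | 4/7 = 57.1% (Visit 4) | 11/14 = 78.6% (Visit 4) |
| 13 | 5/7 = 71.4% (Visit 4) | 12/14 = 85.7% |
| 14 | 6/7 = 85.7% | 25/28 = 89.3% |
| 15-26 | 11/14 = 78.6% (Visit 5) | 25/28 = 89.3% |
| 27, 28 | 12/14 = 85.7% | 39/42 = 92.9% |
| 29-40 | 11/14 = 78.6% (Visit 6) | 39/42 = 92.9% |

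**Start days in breach.**
- Per interval: 12 + 1 + 12 + 12 = 37 of 40. The last 12 appear only at Visit 6, when treatment has ended, so 25 of 40 can lead to a discontinuation.
- Cumulative: 12 of 40.
- Whole period: 0 of 40.
- Both counts that can act during treatment: exactly starts 1-12, the holidays completed by Day 14.

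**Shorter holidays.** A 2-day holiday (41 start days) breaches for 12 starts per interval, for 6 cumulatively (starts 1-6, 5/7 = 71.4%), and for none over the whole period. A 1-day holiday never breaches.

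**Sensitivity to visit timing.** Visit windows are not in the visible text, so these shifts are assumptions.
- If both 14-day intervals run 15 days, compliance there is 12/15 = 80.0%, which is not below the limit. The per-interval total falls to 13 of 42 start days.
- If the Visit 4 count covers 15 days, starts 7-12 reach 80.0% cumulatively and only starts 1-6 breach on that count.
- If the first capsule is taken the morning after Visit 2 and one fewer is expected by Visit 4, the cumulative figure is 10/13 = 76.9% instead of 78.6%.
- With each of the four visits moved by −1, 0 or +1 day (81 patterns), starts 1-12 breach per interval in every pattern and starts 1-5 breach on both counts in every pattern. The share of start days in breach runs from 29.3% to 92.7% per interval and from 12.2% to 30.8% cumulatively.

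**Effect of the unstated choice.** If approved holiday days were left out of the denominator, the same holiday would give 11/11 = 100% at Day 14. These figures show how much depends on the choice. They do not favour one rule.

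**The case against.** The strongest reply is that the sections can be read together. The holiday rule is specific, and the compliance rule is general and aimed at poor compliance. A patient who pauses with the Investigator's agreement is following instructions, and Protocol 9.3.3 lists adverse events and non-compliance as separate discontinuation reasons. The compliance rule says should where the 4-day rule says will. Three days is also a ceiling, so a cap on consecutive days and a percentage floor could both be intended. The formulas that count calendar days serve summaries only, and the cumulative count is named nowhere in the documents. Over 42 days nothing breaches.

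Much of this is fair. The milder reading is possible, and the formulas are not stated to govern the site rule. The cumulative margin for starts 7-12 is thin: one extra day at Visit 4 removes it. The visit-by-visit procedures to which 9.5.5 points are not in the public text, so an instruction there cannot be excluded.

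It does not remove the conflict. The pill-count limits are the only definition of poor compliance shown, and nothing visible directs a site to the milder reading. If should leaves discretion, no criterion for using it is given. A 42-day count is complete only when treatment ends, so it cannot drive a rule meant to act at any time during the study. The per-interval count, which the protocol does name, gives the lowest percentages.

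**Conclusion.** The concern holds and should be fixed. On the nominal schedule, with off-drug days kept in the denominator, every permitted 3-day holiday completed by Day 14 falls below 80% on either count that can act during treatment. Later holidays breach only per interval: at 71.4% for a start on Day 13, otherwise at a marginal 78.6%. The per-interval breach for starts 1-12 survives one-day shifts in any visit. The cumulative breach is equally robust only for starts 1-5.

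The conclusion is limited to the visible text. The documents give no frequency of holidays, so the number of patients affected, any imbalance between arms and any effect on the primary comparison cannot be estimated.

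**What to change.** Reconcile Protocol 9.4.5 and 9.4.9. The text should state:

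1. the period over which the 80% and 120% limits are computed (per visit interval, cumulative to the visit, or whole treatment period);
2. whether days of an approved holiday count in the pill-count percentage.

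Which rule applies is for the sponsor to decide. The cost is a short protocol clarification and a memo to sites, with no extra patients, visits or procedures.
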